### **9.3.8. Events of Special Interest**

#### **9.3.8.1. Gastrointestinal Event**

Subjects taking HTD1801 may experience GI discomfort related to this therapy. This is variously described as diarrhea, abdominal bloating, abdominal discomfort, abdominal pain, and sometimes even constipation. Rather than have the subject discontinue and stop treatment altogether, downward dose titration from the starting dose of HTD1801 2000 mg per day is allowed and even encouraged.

Guidelines for dose reduction in the event of GI discomfort are outlined in Section [6.1.3](#).

#### **9.3.8.2. Treatment Failure due to HTD1801 Dose Reduction**

If any subject with PBC fails treatment after having their dose reduced, their study participation will be terminated and the subject would be able to resume their pre-study treatment for PBC after early termination study-required assessments completed. A subject will be considered to have failed treatment if the serum ALP, after having been lowered on treatment, returns to baseline or higher on two subsequent assessments (baseline is calculated as the average of the historical value and the value at screening).

#### **9.3.8.3. Reporting of Pregnancy**

When any member of the study staff becomes aware of a subject's (or subject's partner's) pregnancy, the site staff must report the pregnancy to the medical monitor and the within 24 hours by using the Pregnancy Notification Form. The female subject will discontinue study medication. The pregnancy will be followed until there is an outcome and the outcome is reported to the sponsor.

## **10. DRUG-INDUCED LIVER INJURY (DILI) MONITORING AND STOPPING RULES**

It is important for study staff to monitor subjects for drug-induced liver injury and to educate subjects to recognize DILI symptoms and seek immediate medical attention.

Liver enzymes and serum bilirubin levels will be assessed at each clinic visit. Elevated ALTs will be assessed and dealt with as shown in [Table 7](#) and [Table 8](#). There are separate DILI monitoring plans based on whether the subject had normal or near normal versus elevated ALT values at baseline, because some subjects with PBC may have normal or near normal ALT levels at baseline. The Medpace Reference Laboratory (MRL) which will serve as the central laboratory for this study has defined its upper limit of normal for ALT as 53 U/L, in both males and females. The study therefore considers up to 60 U/L as being normal or near normal while >60 U/L is considered elevated.

Persistent Cholestatic liver injury is characterized by elevations in serum alkaline phosphatase and/or bilirubin (see [Table 7](#) and [Table 8](#)).

### **10.1. Protocol Definition of Normal or Near Normal and Elevated ALT**

#### **10.1.1. Detection of Potential DILI in Subjects with Normal or Near Normal ALT levels at baseline**

Because some subjects with PBC may have normal or near normal ALT levels at baseline (see Hirschfield 2015), an on-treatment ALT value more than 3x the ULN (i.e. >180 u/L) will be the threshold for triggering the DILI monitoring plan for these subjects.

#### **10.1.2. Detection of Potential DILI in Subjects with Elevated ALT levels at baseline**

Because subjects to be enrolled in the study have underlying liver disease, it is very likely that they may have an elevated ALT level at baseline and therefore multiples of the baseline will be used for DILI monitoring where the baseline value is elevated. The baseline ALT value will be calculated as the average of those obtained at the screening and baseline visits. An on-treatment ALT value more than 3x the baseline value will be the threshold for triggering the DILI monitoring plan for these subjects.

#### **10.1.3. Process for DILI Monitoring**

Serum ALT will be measured as part of a serum chemistry panel at screening, baseline and at weeks 2, 4, 6, 8 and 12. Serum samples will be shipped to a central or local laboratory for testing. Central lab reports will be faxed or emailed to the clinical site within 24 hours of receipt of the sample to be reviewed by the site PI. Local lab results will need to be entered into eDC. Values meeting or exceeding the DILI threshold described in Tables 7 and 8 will be flagged for the attention of the medical monitor. The medical monitor will contact the clinical site to initiate the DILI monitoring protocol.

**Table 7: Liver Monitoring Procedure – For Subjects with Normal or Near Normal Baseline ALT ( $\leq 60$  U/L)**

Event	Observation	Action
ALT becomes elevated	Isolated increase in ALT to $\geq 3$ x ULN (i.e., $\geq 180$ /L) with no increase in serum bilirubin and presence of symptoms of anorexia, nausea, fatigue, right upper abdominal discomfort or vomiting preceding or following the isolated increase in ALT to $\geq 3$ x ULN.	

Promptly repeat serum chemistry panel (ALT, AST, ALP, total bilirubin and direct bilirubin) within 2 to 5 days*

If subject lives remotely from the site, local labs may be obtained

The PI must review the local lab results promptly and local lab results must be entered into an unscheduled visit within the EDC

Continue investigational study drug

ALT remains elevated	If ALT remains $\geq 3$ x ULN	

Obtain serum chemistry panel (as above) and repeat 2 – 3 x/week until stable

Frequency of testing can be decreased to once per week or less if abnormalities stabilize or the subject is asymptomatic

Obtain detailed history of symptoms and prior or concurrent medical history

Obtain history of concomitant drug use including non-prescription medications, herbal & dietary preparations, alcohol use, recreational drug use, and special diets

Where appropriate, rule out acute viral hepatitis types A, B, C, D, & E, autoimmune or alcoholic hepatitis, NASH, hypoxic/ischemic hepatopathy & biliary tract disease

Obtain a history of exposure to environmental chemical agents

Obtain additional tests to evaluate liver function, as appropriate (e.g., INR, CBC with differential)

Continue investigational study drug

ALT decreases	ALT return to $< 3$ x ULN or baseline level	

Resume study-required laboratory assessments as per the Summary of Events table and continue investigational study drug

Elevated Liver Function Tests Worsen or Clinical Symptoms Develop	If ALT is $> 8$ x ULN of baseline on one occasion, or If ALT is $> 5$ x ULN of baseline for more than 2 weeks, or If ALT is $> 3$ x ULN of baseline AND bilirubin is $> 2$ X ULN OR INR $> 1.5$ , or	

Permanently STOP investigational study drug

Continue monitoring until all abnormalities return to normal or to the baseline state

All DILI monitoring results must be recorded in the DILI monitoring eCRF

	If ALT is >3x ULN of baseline AND subject is symptomatic (severe fatigue, nausea, vomiting, right upper quadrant pain or tenderness, fever, rash, and/or eosinophilia (>5%))	
Persistent Cholestatic Liver Injury	If serum ALP is >2x ULN and total and direct bilirubin is >2x ULN	

• Permanently STOP investigational study drug

• Continue monitoring until all abnormalities return to normal or to the baseline state

• All DILI monitoring results must be recorded in the DILI monitoring eCRF

\* The PI must review the local lab results promptly. Local lab results must be entered into an unscheduled visit within the EDC

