**Table 8: Liver Monitoring Procedure – For Subjects with Calculated Baseline ALT >60 U/L (Elevated ALT)**

Event	Observation	Action
ALT becomes elevated	Isolated increase in ALT to $\geq 3$ x ULN (i.e., $\geq 180$ u/L) with no increase in serum bilirubin and presence of symptoms of anorexia, nausea, fatigue, right upper abdominal discomfort or vomiting preceding or following the isolated increase in ALT to $>3$ x ULN.	
 
Promptly repeat serum chemistry panel (ALT, AST, ALP, total bilirubin and direct bilirubin) within 2 to 5 days* 
 
If subject lives remotely from the site, local labs may be obtained
 
The PI must review the local lab results promptly and local lab results must be entered into an unscheduled visit within the EDC
 
Continue investigational study drug
 
 
 

ALT remains elevated	If ALT remains $\geq 3$ x calculated baseline	
 
Obtain serum chemistry panel (as above) and repeat 2 – 3 x/week until stable
 
Frequency of testing can be decreased to once per week or less if abnormalities stabilize or the subject is asymptomatic
 
Obtain detailed history of symptoms and prior or concurrent medical history
 
Obtain history of concomitant drug use including non-prescription medications, herbal & dietary preparations, alcohol use, recreational drug use, and special diets.
 
Where appropriate, rule out acute viral hepatitis types A, B, C, D, & E, autoimmune or alcoholic hepatitis, NASH, hypoxic/ischemic hepatopathy & biliary tract disease
 
Obtain a history of exposure to environmental chemical agents
 
Obtain additional tests to evaluate liver function, as appropriate (e.g., INR, CBC with differential)
 
Continue investigational study drug
 

ALT decreases	ALT return to $<3$ x ULN or baseline level	
 
Resume study-required laboratory assessments as per the Summary of Events table and continue investigational study drug
 

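### Tables 7 and 8 have no row, and so no repeat time, for a first trigger-level ALT with bilirubin risen to between 1x and 2x ULN, INR not above 1.5 and no stop-row symptom

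*Protocol*

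**What the plan says.** Protocol Section 10 routes every raised ALT to two tables: "Elevated ALTs will be assessed and dealt with as shown in" Table 7 (baseline ALT up to 60 U/L) and Table 8 (above 60 U/L). The central laboratory's ULN is 53 U/L, but "The study therefore considers up to 60 U/L as being normal or near normal".

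The entry to the plan depends on ALT only. In Section 10.1.1 an ALT above 180 U/L "will be the threshold for triggering the DILI monitoring plan for these subjects"; Section 10.1.2 does the same at 3x the baseline value. SAP Section 2.3 (Additional Analyses) also defines the liver monitoring threshold by ALT alone.

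The tables then add conditions:

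- **Row 1, first elevation.** ALT at least 180 U/L, "with no increase in serum bilirubin and presence of symptoms of anorexia, nausea, fatigue" and so on; Table 8 repeats "with no increase in serum bilirubin and presence of symptoms of anorexia". Action: repeat the panel within 2 to 5 days and continue drug.
- **Row 2, persisting elevation.** In Table 8, "If ALT remains $\geq 3$ x calculated baseline"; Table 7 is the same with ULN. Action: test two to three times a week until stable.
- **Row 3.** ALT falls.
- **Row 4, permanent stop.** ALT above 8x once; above 5x for more than 2 weeks; above 3x with bilirubin above 2x ULN or INR above 1.5; or above 3x and "symptomatic (severe fatigue, nausea, vomiting, right upper quadrant pain or tenderness, fever, rash, and/or eosinophilia".
- **Row 5, cholestatic stop.** "If serum ALP is >2x ULN and total and direct bilirubin is >2x ULN".

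**The concern.** A rise in ALT together with a rise in bilirubin is the pattern that row 4 turns into a permanent stop once bilirubin passes 2x ULN. A subject part of the way there is the one for whom an early repeat is most informative. Yet the bilirubin condition in row 1 shuts that subject out of the only timed repeat, and no other row takes the subject in. What is at stake is how soon a possible liver injury is rechecked while dosing continues. The ALP efficacy analysis is not involved.

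**Working it through.** The plan gives no figure to reproduce; this is a check of whether the rows cover all cases.

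**Inputs.** Bilirubin ULN 1.21 mg/dL (SAP Section 2.3.2), so 2x ULN = 2 × 1.21 = 2.42 mg/dL. ALT ULN 53 U/L and working limit 60 U/L (Protocol Section 10). The printed 180 U/L is 3 × 60; 3 × 53 would be 159. On-treatment chemistry is at Weeks 2, 4, 6, 8 and 12. INR is scheduled at Screening, Weeks 6 and 12 and early termination, so not at Weeks 2, 4 or 8 (Table 1).

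**The case.** First on-treatment ALT at the trigger and below the single-value stop limit; bilirubin risen from baseline to above 1.21 but not above 2.42 mg/dL; INR at most 1.5 or not measured; no stop-row symptom or sign.

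- Row 1: not met. Bilirubin has increased, whether that means above ULN or above the subject's baseline, so the reading of the symptom clause does not matter.
- Row 2: not met; it needs a second value.
- Row 3: not met; nothing has fallen.
- Row 4: not met. ALT is below 8x, a first value cannot show 2 weeks' duration, bilirubin is not above 2x ULN, INR is not known to exceed 1.5, and there is no listed symptom.
- Row 5: not met; bilirubin is not above 2x ULN.

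**How wide is it?** Take ALT at 4, 6 and 7.9 times the limit, bilirubin at 1.5 and 2.0 times ULN, INR 1.0 and 1.6, and symptoms absent or present: 3 × 2 × 2 × 2 = 24 combinations. The 6 with INR 1.0 and no symptoms meet no row. The other 18 meet row 4. These are counts of cases, not probabilities.

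**The same ALT with normal bilirubin (e.g. 0.7 mg/dL) and INR at most 1.5** depends on how the symptom clause in row 1 is read:

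| Reading of the clause | No symptoms | Anorexia or non-severe fatigue |
|---|---|---|
| Symptoms required (literal) | no row | row 1 |
| Meant as no symptoms | row 1 | no row |
| Ignored | row 1 | row 1 |

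With bilirubin 2.0 mg/dL all six cells are empty.

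**ALT band.** The lower end is 180 U/L in Table 7 and, from the Section 10.1.2 trigger, 3 × 61 = 183 or 3 × 100 = 300 U/L in Table 8. The upper end depends on the stop limit, which is written as a multiple of the ULN of (calculated) baseline:

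| Reading of 8x | Table 7, baseline 30 | Table 7, baseline 60 | Table 8, baseline 61 | Table 8, baseline 100 |
|---|---|---|---|---|
| 8 × 53 = 424 | 180–424 | 180–424 | 183–424 | 300–424 |
| 8 × 60 = 480 | 180–480 | 180–480 | 183–480 | 300–480 |
| 8 × own baseline | 180–240 | 180–480 | 183–488 | 300–800 |

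**Time to the next scheduled panel.** Weeks 2 to 4, 4 to 6 and 6 to 8: 14 days. Weeks 8 to 12: 28 days. Row 1 would give 2 to 5 days.

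**The case against.** The best defence is that this subject is not overlooked. The ALT trigger alone flags the value, and the medical monitor contacts the site to start the plan (Section 10.1.3). Investigators must review central laboratory results (9.2.6) and follow clinically significant abnormalities (9.3.1, 9.3.4). Unscheduled visits are allowed (Section 8), and drug must stop for an adverse event that threatens safety (7.2). A site would probably treat row 1 as the first step from its label alone, and a second raised value enters row 2, which has no bilirubin or symptom condition.

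Most of this stands. A reader might infer that these subjects wait 14 or 28 days for a test; the documents do not support that, because such a delay needs both the medical monitor and the investigator to order nothing after a flagged value. What does not stand is that the other text closes the gap. None of those sections gives an interval for the repeat. The only other extra testing, every 2 to 4 weeks, is for subjects whose dose was reduced (6.1.3, 7.1). And the plan that the monitor is to start is the tables, whose first step excludes this subject by its stated condition.

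A reader might also infer that the tables always put the lower-risk subject first. That depends on the symptom clause. If it means no symptoms or is ignored, an asymptomatic ALT rise with normal bilirubin gets the timed repeat and the same ALT with raised bilirubin does not. Read literally, the asymptomatic subject with normal bilirubin is uncovered too, and the reversal is confined mainly to subjects with anorexia or non-severe fatigue.

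**Conclusion.** The gap is real and narrow: it needs every condition in the case above, and for that subject the plan raises a flag but sets no repeat time.

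Two wider readings fail. One is that any first ALT elevation with bilirubin between 1x and 2x ULN falls through; row 4 already stops drug for those with a listed symptom or INR above 1.5. The other is that ALT as high as 800 U/L is left without a rule; that holds only if the stop limit is 8x the subject's own baseline. On either ULN reading, Table 8 values such as 488, 600 and 800 U/L already mean a permanent stop.

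The documents give no rate for this pattern, and among up to 30 subjects there may be few or none. The conclusion rests on the printed row conditions and on the central laboratory's bilirubin ULN; it does not depend on the reading of the symptom clause. Severity: minor to should-fix.

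**What to change.** - **Table 7, row 1:** order the 2-to-5-day repeat for any ALT of at least 180 U/L that meets no stop criterion, regardless of bilirubin or symptoms.
- **Table 8, row 1:** order it for any ALT of at least 3x calculated baseline that meets no stop criterion, regardless of bilirubin or symptoms. If the present 180 U/L entry is kept as well, remove its bilirubin condition. Otherwise, at baseline 100 and ALT 250 U/L (below the 300 U/L trigger), a subject with bilirubin 0.7 mg/dL could get the repeat while one with 2.0 mg/dL could not.
- While the rows are open, say which limit the stop multiples refer to, since the new wording relies on the stop criteria.

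The cost is a wording change in two table rows and a few extra chemistry panels.

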## 1.2. Schema

Optional Pre-Screening for ALP	Screening	Baseline Initiate IP Dosing	IP Dosing HTD1801 1000 mg BID					Follow-Up End of Study
Day -56 to Day -28	Day -28 to Day -1	Day 0	Week 2 Day 14 ±3 days	Week 4 Day 28 ±3 days	Week 6 Day 42 ±3 days	Week 8 Day 56 ±3 days	Week 12 Day 84 ±3 days	Week 16 Day 112 ±5 days

PK Sampling:  
-30 minutes prior to dosing,  
4 hours ±30 minutes and  
8 hours ±30 minutes post-dosing  
for subset of at least 6 subjects

PK Sampling:  
-30 minutes prior to dosing,  
4 hours ±30 minutes and  
8 hours ±30 minutes post-dosing  
for subset of at least 6 subjects

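### Tables 7 and 8 let absence of symptoms alone relax testing while ALT is still at least 3x and drug continues, with no minimum frequency; at weekly testing a stop limit is found about 3–5 days later

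*Protocol*

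**What the plan says.** The row for ALT that remains elevated (second row of Tables 7 and 8, protocol Section 10.1.3) applies while ALT is at least 3x ULN (Table 7) or at least 3x calculated baseline (Table 8). Study drug continues. The first action is a chemistry panel, then "repeat 2 – 3 x/week until stable". A later bullet, identical in both tables, reads: "Frequency of testing can be decreased to once per week or less if abnormalities stabilize or the subject is asymptomatic".

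Four other places bear on this:

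- **Entry to the plan.** Section 10.1.1: "an on-treatment ALT value more than 3x the ULN (i.e. >180 u/L) will be the threshold for triggering the DILI monitoring plan". Section 10.1.2: "An on-treatment ALT value more than 3x the baseline value will be the threshold for triggering the DILI monitoring plan for these subjects". Neither mentions symptoms, although the first row of each table does.
- **Fixed testing.** Section 10.1.3: "Serum ALT will be measured as part of a serum chemistry panel at screening, baseline and at weeks 2, 4, 6, 8 and 12". The schema (Section 1.2) gives "Week 8 Day 56 ±3 days" and "Week 12 Day 84 ±3 days".
- **Stop row.** Drug stops permanently if ALT is above 8 "x ULN of baseline on one occasion" (Table 8 refers to calculated baseline), above 5x for more than two weeks, above 3x with bilirubin above 2x ULN or INR above 1.5, or above 3x with listed symptoms.
- **Return to the visit schedule.** The third row allows this once ALT has fallen.

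**The concern.** The default says to test intensively until the abnormality is stable. The step-down joins stability and absence of symptoms with *or*, so a subject with no symptoms qualifies whatever the ALT trend. That undercuts the instruction it qualifies. The words *or less* then leave the lower end of the frequency open.

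Absence of symptoms says little about the laboratory stop limits; only a panel shows whether one has been crossed. The relaxation is also open to many of the subjects it matters for. ALT above 3x with listed symptoms such as severe fatigue, nausea or vomiting already stops drug, so those still on drug in this row are largely those without such symptoms. At stake is extra time on study drug after a stop limit has been crossed but not yet measured.

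**Working it through.** The plan states no figure to reproduce. The check has two parts: what the wording permits, and how much later a stop limit would be found.

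**Inputs**

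- On-treatment visits with ALT: days 14, 28, 42, 56 and 84, each ±3 days (Sections 1.2 and 10.1.3).
- Default frequency while ALT is at least 3x: two to three panels a week (Tables 7 and 8, second row).
- Repeat panel 2 to 5 days after the first elevated value (first row).
- Stop limits (fourth row). Their wording mixes ULN and baseline, but the delays below depend only on panel spacing.
- Assumption: panels are spread evenly on whole days. Three a week gives gaps of 2, 2 and 3 days, two a week gives 3 and 4, and weekly gives 7.

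**Limits met on a single panel (above 8x; above 3x with bilirubin above 2x ULN).** The longest wait from crossing the limit to the next panel is the longest gap.

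| Testing | Longest wait (days) | Added to default (days) |
|---|---|---|
| 2–3 per week | 3–4 | – |
| Weekly | 7 | 7−4 = 3 to 7−3 = 4 |
| Visits only, to Week 8 | 14 | 14−4 = 10 to 14−3 = 11 |
| Visits only, Week 8 to 12 | 84−56 = 28 | 28−4 = 24 to 28−3 = 25 |

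With windows, the visit gaps become (28+3)−(14−3) = 20 days and (84+3)−(56−3) = 87−53 = 34 days.

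**Duration limit (above 5x for more than two weeks).** Let day 0 be the first panel above 5x. The rule can first be confirmed on the first panel after day 14.

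- Three a week: 14+2 to 14+3 = day 16–17.
- Two a week: 14+3 to 14+4 = day 17–18.
- Weekly: day 21, which is 21−18 = 3 to 21−16 = 5 days later than the default.
- Visits only, for a subject already stepped down whose first panel above 5x is at Week 8: day 28, which is 28−18 = 10 to 28−16 = 12 days later (day 34 with windows, 16 to 18 later).

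The last case does not describe a subject who first reaches 3x at Week 8. The required repeat on day 2–5 leaves 28−5 = 23 to 28−2 = 26 days to Week 12.

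**Does other text set a shorter interval?** Sections 6.1.3 and 7.1 give 2 to 4 weeks, for dose-reduced subjects only, which is no tighter than the visit schedule. The third row implies extra testing until ALT falls but names no interval. Nothing else requires a panel before the next visit once the step-down is used.

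**The case against.** The strongest reply is that the clause only permits a reduction. A reader might infer that absence of symptoms ends the intensive schedule. The text does not say so: the site may keep testing two to three times a week.

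A reader might also infer that the plan leaves such subjects untested for up to 28 days. That needs *or less* to mean visits only. The third row returns subjects to the scheduled assessments once ALT has fallen, which would have little purpose if they were already on visit-only testing. This objection stands against leading with 14 or 28 days. It does not supply a minimum.

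The number affected is uncertain. The first row of each table includes symptoms, so a subject who came through it may be asymptomatic only because symptoms resolved. Sections 10.1.1 and 10.1.2 trigger on ALT alone, so subjects who never had symptoms can also enter. The documents do not settle the mix.

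Safeguards exist: the 2-to-5-day repeat, flagging of threshold values to the medical monitor (10.1.3), investigator review of central results (9.2.6), unscheduled visits (Section 8), education of subjects about symptoms (Section 10), and the stop rule for ALT above 3x with symptoms. They reduce the risk. However, they act on results already drawn, on discretion or on symptoms, and none obliges a site to draw the next panel from a symptom-free subject before the next visit.

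**Conclusion.** The point holds as a wording gap in a safety rule. While ALT is still at least 3x and drug continues, absence of symptoms alone permits leaving the default schedule, and no minimum frequency applies. At the frequency the clause names, weekly, the cost is about 3 to 5 days in finding a laboratory stop limit, assuming evenly spaced panels. Intervals of 14 to 28 days (20 to 34 with windows) are a worst case that depends on visit-only testing. The documents suggest this was not intended but do not exclude it.

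The size rests on panel spacing only. No rate of ALT rise and no number of affected subjects can be taken from the documents. This is a cheap patient-safety improvement; it has no effect on the efficacy analysis.

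**What to change.** Make two wording edits in the second row of both tables:

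- Delete the no-symptoms alternative, so that step-down requires stable abnormalities.
- Replace the open-ended frequency with: no less than once per week while ALT remains ≥3x ULN (Table 7) or ≥3x calculated baseline (Table 8).

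Absence of symptoms should not be added as a second requirement. Fatigue is common in PBC (Section 2.1.1) and would hold stable subjects at two to three panels a week.

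The cost is extra chemistry panels in the few subjects with sustained elevation. Per 28 days the default gives 8–12 panels, weekly testing 4, and the visit schedule after Week 8 gives 1. The change therefore adds 8−4 = 4 to 12−4 = 8 panels over weekly testing while ALT is unstable, and at most 4−1 = 3 over visit-only testing once it is stable. INR is drawn in this row only as appropriate, so the INR criterion is not found sooner.

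The differing ALT limits within Table 8 should not be altered as part of this edit. Changing its third row alone could put a subject with baseline 100 U/L and ALT 180–299 U/L under both the first row and a return to visit-only testing. Any alignment must change the first and third rows together and is a separate point.

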### 7.2. Discontinuation of Study Intervention

HTD1801 treatment must be discontinued for a subject if any of the following criteria are met.

- Adverse event that may jeopardize subject's safety
- Grade 3 and above adverse events (AEs) for which the causality is considered as related to investigational agent
- Discontinuation due to drug-induced liver injury (refer to Section 10)
- Request by the subject
- Pregnancy

For subjects who discontinue investigational study drug, an Early Termination Visit should be conducted at the time the investigational study drug is discontinued (see Section 7.3). Subjects who terminate from the study prior to Study Visit Week 12 will be requested to return to the clinic 28 days **after the date of last dose** of investigational study drug and complete the equivalent of the Week 16 follow up visit assessments. If necessary, arrangements can be made with the site and the subject to conduct the visit virtually and make use of a local laboratory for the study required Study Visit Week 16 lab tests.

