**Table 4 Classification of Adverse Events (AEs) by Severity**

Severity a	Definition
Mild AE (Grade 1)	Mild; asymptomatic or mild symptoms; clinical or diagnostic observations only; intervention not indicated.
Moderate AE (Grade 2)	Moderate; minimal, local or noninvasive intervention indicated; limiting age-appropriate instrumental activities of daily living
Severe AE (Grade 3)	Severe or medically significant but not immediately life-threatening; hospitalization or prolongation of hospitalization indicated; disabling; limiting self care activities of daily living
Life-threatening or disabling AE (Grade 4)	Life-threatening consequences; urgent intervention indicated.
Death related to AE (Grade 5)	Death related to AE.

a From Common Terminology Criteria for Adverse Events, Version 5.0

Any AE that changes in severity or grade during a single occurrence of an AE will be recorded in the eCRF at the highest level experienced by the subject.

An AE that is assessed as severe should not be confused with an SAE. Severity is a category used for rating the intensity of an AE (such as mild, moderate, or severe myocardial infarction). However, an AE itself may be of relatively minor medical significance, such as a severe headache. Both AEs and SAEs can be assessed as severe. An AE is considered serious when it meets one of the predefined outcomes described in Section 9.3.2.

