Elevated Liver Function Tests Worsen	If ALT is $>8$ x ULN of calculated baseline on one occasion, or If ALT is $>5$ x ULN of calculated baseline for more than 2 weeks, or If ALT is $>3$ x ULN of calculated baseline AND bilirubin is $>2$ X ULN OR INR $>1.5$ , or	
 
Permanently STOP investigational study drug
 
Continue monitoring until all abnormalities return to normal or to the calculated baseline state
 
All DILI monitoring results must be recorded in the DILI monitoring eCRF
 

	If ALT is >3x ULN of calculated baseline AND subject is symptomatic (severe fatigue, nausea, vomiting, right upper quadrant pain or tenderness, fever, rash, and/or eosinophilia (>5%))	
Persistent Cholestatic Liver Injury	If serum ALP is >2x ULN and total and direct bilirubin is >2x ULN	

• Permanently STOP investigational study drug

• Continue monitoring until all abnormalities return to normal or to the calculated baseline state

• All DILI monitoring results must be recorded in the DILI monitoring eCRF

\* The PI must review the local lab results promptly. Local lab results must be entered into an unscheduled visit within the EDC

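### DILI Tables 7 and 8 say both continue and permanently stop for a subject with ALT above 3x, no bilirubin rise and current nausea or vomiting, and no sentence says which row prevails

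*Protocol*

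**What the plan says.** **Table 7 (baseline ALT up to 60 U/L).**
- Row 1 describes an isolated ALT rise to at least 3x ULN, printed as 180 U/L, "with no increase in serum bilirubin and presence of symptoms of anorexia, nausea, fatigue, right upper abdominal discomfort or vomiting preceding or following" that rise. The action is to repeat the chemistry panel in 2 to 5 days and continue drug.
- Row 2 applies if ALT stays at 3x ULN or more. It adds closer testing and work-up, and again continues drug. It does not exclude symptomatic subjects: "Frequency of testing can be decreased to once per week or less if abnormalities stabilize or the subject is asymptomatic".
- The last ALT row requires permanent discontinuation on any of four criteria. The fourth is "If ALT is >3x ULN of baseline AND subject is symptomatic (severe fatigue, nausea, vomiting, right upper quadrant pain or tenderness", followed by fever, rash and eosinophilia.

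**Table 8 (calculated baseline ALT above 60 U/L).** Row 1 keeps the 180 U/L figure and the wording "with no increase in serum bilirubin and presence of symptoms of anorexia, nausea, fatigue, right upper abdominal discomfort or vomiting", and continues drug. Row 2 uses 3x calculated baseline and continues drug. The stop row includes "If ALT is >3x ULN of calculated baseline AND subject is symptomatic (severe fatigue, nausea, vomiting" and the same further symptoms.

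**Surrounding text.**
- Section 7.2 makes stopping mandatory when any one listed criterion is met. The list includes "Discontinuation due to drug-induced liver injury (refer to Section 10") and, separately, "Grade 3 and above adverse events (AEs) for which the causality is considered as related to investigational agent".
- Section 10 gives the central-laboratory ALT ULN as 53 U/L and treats values up to 60 as normal or near normal.
- Section 10.1.1 sets the trigger at more than 3x ULN, printed as 180. Section 10.1.2 sets it at more than 3x the average of the screening and baseline values.
- Section 10.1.3 sends flagged values to the medical monitor, who starts the monitoring procedure.
- SAP 2.3 counts subjects crossing 3x ULN (baseline up to 60) or 3x baseline (above 60). It prints no U/L figure for 3x ULN.

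**The concern.** The same result in the same subject fits a row that keeps the subject on drug and a row that removes the drug for good. Two sites following the text exactly could act in opposite ways, and the stop cannot be reversed. The medical monitor is alerted but is referred to the same tables. Section 13.5 allows departures from procedures only to remove an immediate risk, so either action departs from one printed row.

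The overlapping symptom may be common. Section 2.3.1 names nausea among the most frequent treatment-related events, more so at 1000 mg BID, the dose used here. It gives no severity and says the drug was well tolerated.

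The ALT limits add to the uncertainty. One label does not match its number, one row contradicts the section it implements, and the stop rows multiply a quantity that is not defined.

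**Working it through.** This is a conflict between rules, so the first check sets the rows side by side.

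| | Row 1: continue | Row 2: continue | Symptomatic stop |
|---|---|---|---|
| ALT, Table 7 | ≥180 U/L | stays ≥3x ULN | >3x 'ULN of baseline' |
| ALT, Table 8 | ≥180 U/L | stays ≥3x calculated baseline | >3x 'ULN of calculated baseline' |
| Bilirubin | no rise | no condition | no condition |
| Nausea, vomiting | listed | not excluded | listed |
| Timing of symptoms | before or after the rise | not stated | present now |
| Earlier ALT value needed | no | yes | no |

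**Step 1: ALT values that meet both rows.** Let b be baseline ALT. The stop limit can be read as 3 x 53 = 159, 3 x 60 = 180, or 3b.
- Table 7, b ≤ 60: 3b ≤ 180, so ALT above 180 meets row 1 and exceeds all three limits. On the 3b reading, baselines of 22 or less meet the single-occasion 8x stop before ALT reaches 180 (8 x 22 = 176). That sets a second stop criterion against row 1 and does not remove the conflict.
- Table 8, b > 60: 3b > 180, so ALT above 3b meets row 1 and, if it persists, row 2, and exceeds all three limits. At b = 100 this is ALT above 300. Between 180 and 3b, only row 1 applies if the stop is read as a multiple of baseline.

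**Step 2: symptoms that meet both rows.** Nausea and vomiting are on both lists. Anorexia is only in row 1. Fatigue overlaps only if severe.
- If 'severe' qualifies fatigue alone, any current nausea or vomiting overlaps.
- If it qualifies the whole list, only severe nausea or vomiting does. Table 4 equates severe with Grade 3, and Section 7.2 already stops drug for related Grade 3 events.
- If 'no' in row 1 was meant to cover symptoms as well as bilirubin, row 1 drops out and the conflict moves to row 2. Otherwise row 1 has no asymptomatic case, although 10.1.1 and 10.1.2 trigger on ALT alone.

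**Step 3: the ALT reference for baseline up to 60.**

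| Reference | 3x | 5x | 8x |
|---|---|---|---|
| ULN 53 | 159 | 265 | 424 |
| Cut 60 | 180 | 300 | 480 |
| Difference | 21 | 35 | 56 |

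The printed 180 is 3 x 60. SAP 2.3 applied to the central-laboratory range in SAP 2.3.2 (upper limit 53) gives 3 x 53 = 159.

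**Step 4: Table 8 limits.** Row 1 says 180. Section 10.1.2 and row 2 give 3 x 61 = 183, 3 x 100 = 300 and 3 x 150 = 450 at those baselines. For the stop row at b = 150, 8x is 1200 U/L as a multiple of baseline and 8 x 53 = 424 as a multiple of ULN. The second lies below the 3x-baseline trigger of 450. The 3x ULN limit of 159 lies below that trigger for every Table 8 subject, since even b = 61 gives 183.

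**The case against.** The best defence is that the intent is clear. Section 7.2 makes stopping mandatory if any listed criterion is met, Section 10 is titled as containing stopping rules, and the rows escalate: ALT rises, stays up, falls, then worsens or symptoms develop. Read that way, the last row overrides. This has force, and most clinicians would probably stop. But 7.2 only points back to Section 10, and no sentence ranks the rows. The symptomatic criterion needs no earlier value and no persistence. Table 7's stop-row label mentions symptoms; Table 8's mentions only worsening, so the escalation argument is stronger for Table 8.

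Row 1 also covers symptoms before or after the rise, while the stop row needs a subject who is symptomatic now. Past or later symptoms fit row 1 alone. This stands, and limits the conflict to current symptoms.

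Review by the medical monitor makes divergence between sites less likely, and 7.2 separately stops drug for any event that may jeopardise safety. Both points lower the severity. For baseline up to 60, the printed 180 also makes the monitoring trigger workable despite its label.

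A reader might infer that row 2 tells sites to keep dosing above 8x, or with bilirubin above 2x ULN, because row 2 has no upper limit. The documents do not support that: read with 7.2, the row order only makes sense as escalation. A reader might also infer that the SAP prints 159. It prints 3x ULN, and local results, whose ULN may differ, are used too.

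**Conclusion.** The conflict is real and limited. It needs ALT above 180 U/L (Table 7) or above 3x calculated baseline (Table 8), no bilirubin rise, and current nausea or vomiting. The ALT part holds on every reading of the stop limit. The symptom part depends on what 'severe' covers, and on the wider reading the residual conflict is small. Section 7.2 and the row order favour stopping without saying so.

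This should be fixed, because it is an irreversible safety rule. It does not rank higher: the likely intent can be inferred, at most 30 subjects are planned, and the documents give no rate of ALT above 3x, so the number affected cannot be estimated.

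A reader might infer bias in the Week 12 result, since a subject taken off drug leaves that analysis. Nothing in the documents allows such an effect to be shown, and none is claimed. Nor is the SAP's use of the last pre-dose ALT, in place of the screening/baseline average, a hidden inconsistency. SAP 2.4.1 discloses it, and it needs no change.

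**What to change.** 1. In 10.1.3 and both tables, state that any met stop criterion overrides the continue action in rows 1 and 2. Say whether 'severe' applies to nausea and vomiting. Limit row 1 to subjects without current stop-list symptoms. Use the same inequality (≥ or >) in the trigger and the symptomatic stop, or a subject exactly at the limit with nausea would fall in neither row.
2. For baseline ALT up to 60, use one reference for trigger and stop limits in 10.1.1, Table 7 and SAP 2.3: either 180/300/480 U/L (multiples of 60) or 159/265/424 U/L (multiples of 53). Mixing them, with a trigger of 180 and a stop at 3 x 53, would permanently stop a symptomatic subject at ALT 160 to 179, below the trigger.
3. Change Table 8 row 1 from 180 U/L to at least 3x calculated baseline, to match 10.1.2 and row 2.
4. Replace the undefined multiple in the stop rows with one defined reference. For Table 8 the clinical team must choose, because the 8x limit at baseline 150 is 1200 or 424 U/L depending on the reading, and the lower figure is below the trigger.

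The cost is a protocol amendment to 10.1.1, 10.1.3 and Tables 7 and 8, with IRB/IEC approval and regulatory submission under 13.5, and one line in SAP 2.3. It adds no scheduled visits, tests or subjects.
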